5.2.3 Safety Analysis Set

The SafAS is defined as those subjects who have received study vaccine and for which safety data are scheduled to be collected. All subjects will have their safety analyzed after each dose according to the vaccine they actually received. For the analysis at any dose, subjects will be analyzed according to the treatment received at the first dose.

Safety data recorded for a vaccine received out of the protocol design will be excluded from the analysis (and listed separately).

5.2.4 Other Analysis Set(s)

Screened subjects: all subjects with a Screening Visit.

Randomized subjects: a randomized subject is a subject for whom an injection group has been allocated.

5.2.5 Populations Used in Analyses

The SafAS will be used for the description of clinical safety data. Subjects will be analyzed according to the product they actually received.

The immunogenicity analyses will be performed on the PPAS and will be confirmed on the FAS.

Screened subjects and randomized subjects will be used for various standard population tables including duration of the study, disposition of participants and deviations. Demographic and baseline characteristics will be presented on the PPAS, FAS and SafAS.

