9.3 Observational Endpoints and Assessment Methods

9.3.1 Immunogenicity

9.3.1.1 Immunogenicity Endpoints

- Anti-NS1 IgG at baseline
- Neutralizing Ab levels against YF at baseline
- Neutralizing Ab levels against Zika at baseline

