2.3 Observational Objective

Immunogenicity

- To describe the FV (dengue, YF and Zika) serological status in the study population at baseline.

3 Description of the Overall Trial Design and Plan

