3.1 Trial Design

This is a multicenter, observer-blind, randomized, placebo-controlled, Phase II study of the CYD dengue vaccine in 150 HIV-positive adults (18 to 50 years) in Brazil. Potential participants fulfilling all inclusion criteria, including a previous exposure to dengue according to a Rapid Diagnosis Test (RDT) or a dengue IgG enzyme-linked immunosorbent assay (ELISA), will be enrolled. Subjects will receive 3 injections of either CYD dengue vaccine or placebo at 0, 6, and 12 months. The enrollment of subjects will be carried out in two steps, including an early safety data review before the second step.

Subjects HIV-positive and previously exposed to dengue according to RDT or ELISA will be randomized in a 2:1 ratio into 1 of 2 groups:

- Group 1 (N=100): subjects will receive 3 doses of CYD dengue vaccine (live, attenuated, dengue serotype 1, 2, 3, 4 virus)
- Group 2 (N=50): subjects will receive 3 doses of placebo (NaCl 0.9%)

Each subject will have her / his dengue serostatus confirmed using both dengue PRNT and anti-NS1 IgG assay on the pre-injection blood sample. Subjects who are dengue-positive by RDT or ELISA at Screening Visit and dengue-negative by PRNT (sample collected before the first injection [at Visit 1] and assayed before second injection) will be considered as not previously exposed. Therefore, they will not receive any further injections and will be followed for safety until 6 months after the last dose. In addition, if they received the vaccine, provisions for timely access to medical care will be offered for 10 years after the last dose, according to IDMC prior recommendations.

All subjects are planned to be included in safety and immunogenicity analysis set. Blood samples will be taken at the Screening Visit (serology, hematology and biochemistry) if such a visit is required, and at several other time points throughout the study for baseline dengue, YF, and Zika serological status, CYD dengue vaccine immunogenicity, dengue vaccinal viremia post-Inj 1, and HIV status monitoring assessments, depending on the time points.

The duration of each subject's participation in the study will be approximately 18 months.

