5.1.2.2 Statistical Methods

For descriptive purposes, the statistics presented on Table 5.1 will be produced.

The proportion of subjects with a detected and quantified CYD dengue vaccinal viremia (ie, above the detection level) whatever the serotype (as assessed by YF RT-PCR) and for each of the four dengue serotypes (by serotype-specific CYD RT-PCR method) after the first CYD dengue vaccine injection will be presented at V02 and V03.

Number of subjects and percentages having a decrease in CD4 > 30% post-injection compared to pre-injection values and confirmed decrease in CD4 > 30% after each injection, not explained by non-adherence to ART and not explained by any other possible etiology, as well as an increase in HIV viral load post-injection and confirmed increase in HIV viral load (ie, plasma HIV-1 RNA < 50 copies/mL pre-injection and > 1000 copies/mL post-injection) for each injection, not explained by non-adherence to ART and not explained by any other possible etiology will be presented.

Analysis of dengue neutralizing antibody levels will be performed in each vaccine group before first injection (at baseline) and 28 days after each injection using:

- GMTs against each serotype with the parental dengue virus strains
- GM of individual titer ratio (GMTR) against each serotype with the parental dengue virus strains (post-Injection 1/pre-Injection 1, post-Injection 2/pre-Injection 1, and post-Injection 3/pre-Injection 1)
- Number and percentage of subjects ≥ 10 (1/dil) against each dengue serotype with the parental dengue virus strains at each available time point
- Number and percentage of subjects ≥ 10 (1/dil) against at least 1, 2, 3, or 4 dengue serotypes with the parental dengue virus strains at each available time point
- Number and percentage of subjects \geq various titer thresholds (1/dil) against each dengue serotype with parental dengue virus strains at each available time point
- Number and percentage of subjects \geq various titer thresholds (1/dil) for at least 1, 2, 3, or 4 serotypes with parental dengue virus strains at each available time point
- Distribution of titers against each of the 4 serotypes with parental dengue virus strains at each available time point and corresponding RCDCs
- Number and percentage of subjects immune and non-immune to YF, dengue, Zika and FV statuses at baseline

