5.2.1 Full Analysis Set

The FAS is defined as the subjects who received either CYD dengue vaccine or placebo and had blood sample drawn and valid post-injection serology results (ie, a result different from “not-reportable” [“NR”] or missing, for at least one dengue serotype).

Subjects will be analyzed by the vaccine treatment group to which they were randomized.

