5.2.2 Per-Protocol Analysis Set

The PPAS is a subset of the FAS. The subjects presenting with at least one of the following relevant protocol deviations will be excluded from the PPAS:

- Subject did not meet all protocol-specified inclusion criteria or met at least one of the protocol-specified exclusion criteria
- Subject did not complete the vaccination schedule
- Subject received a vaccine other than the one that he / she was randomized to receive
- Preparation and / or administration of vaccine was not done as per-protocol
- Subject did not receive vaccine in the proper time window
- Subject did not provide post-dose serology sample in the proper time window or a post-dose serology sample was not drawn
- Subject received a protocol-prohibited medication (see protocol Section 6.7)
- Subject’s post-injection serology sample did not produce a valid test result (ie, a result different from “NR” or missing, for at least one dengue serotype)
- Subject had other protocol violations that affected the subject’s immune response, as determined by the clinical team before locking the database.

Subjects will remain in the corresponding population as long as they do not meet one of the above criteria.

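### The baseline flavivirus serostatus table defaults to the PPAS, a set selected on post-baseline data and, read literally, on baseline dengue PRNT

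*SAP*

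**What the plan says.** SAP 2.3 gives the observational objective under an immunogenicity heading: "To describe the FV (dengue, YF and Zika) serological status in the study population at baseline". The protocol lists its endpoints (anti-NS1 IgG, YF and Zika neutralizing antibodies at baseline) under "9.3.1.1 Immunogenicity Endpoints". SAP 5.1.2.2 places the matching table among the dengue antibody analyses: "Number and percentage of subjects immune and non-immune to YF, dengue, Zika and FV statuses at baseline". SAP 5.1.3.2, the methods section for the observational objective, names no analysis set.

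The general rule is in SAP 5.2.5: "The immunogenicity analyses will be performed on the PPAS and will be confirmed on the FAS". It makes no exception for endpoints measured only at baseline. The same section adds: "Demographic and baseline characteristics will be presented on the PPAS, FAS and SafAS". It does not say whether flavivirus status counts as a baseline characteristic.

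The two sets are defined as follows:

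- **FAS (SAP 5.2.1):** the subject must have been injected and "had blood sample drawn and valid post-injection serology results", for at least one dengue serotype.
- **PPAS (SAP 5.2.2):** a subset of the FAS. Exclusions include "Subject did not complete the vaccination schedule", doses outside the window, and post-dose samples that are late or not drawn.

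SAP 3.1 deals with subjects who screened positive by rapid test or ELISA but are negative by PRNT on the Visit 1 sample. They are treated as not previously exposed: "Therefore, they will not receive any further injections and will be followed for safety until 6 months after the last dose".

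**The concern.** A description of a population at baseline should not depend on what happened later. Under the default rule, the lead table leaves out subjects for reasons unrelated to the Visit 1 sample, such as a late dose or a missed post-dose bleed.

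For dengue the problem goes further. A negative baseline PRNT stops the injections, the stop leaves the schedule incomplete, and an incomplete schedule is a listed PPAS exclusion. Selection into the lead table then depends on baseline dengue serology, which is close to the quantity being described.

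The subjects removed are those the screening tests classed as previously exposed and the PRNT did not. The protocol (1.2 and 1.3.2) describes people not previously exposed as being at increased risk of hospitalized and severe dengue after vaccination. How many of them entered the trial is a natural thing to read from this table.

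**Working it through.** **No plan figure to reproduce on this point.** The documents give no expected serostatus, PRNT-negative rate or loss rate. The only sample-size figure is a 95% chance of seeing an event of 3% incidence in 100 vaccinees. It reproduces (1 − 0.97^100 = 0.952) and is not in question.

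**Step 1. Which set applies?** The objective and its endpoints are headed immunogenicity, the table sits in the immunogenicity list, and the methods section names no set. SAP 5.2.5 is then the only rule that covers it: PPAS first, FAS as confirmation.

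**Step 2. Does the derivation need post-baseline data?** No. SAP 4.4.2.3 derives status from the pre-vaccination Visit 1 sample for all subjects.

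**Step 3. Whom does the PRNT stop remove?**

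- *PPAS:* a stopped subject receives injection 1 only and literally meets the incomplete-schedule exclusion.
- *FAS:* the stop acts before injection 2 (Month 6). The post-injection 1 sample is drawn at Visit 4, 28 days after injection 1 (Protocol 9.2.2.2). A stopped subject with a valid Visit 4 result stays in.
- *Protocol 12.2.3:* this defines a per-protocol set for each vaccination, so a stopped subject could remain in the dose-1 set. SAP 5.2.2 omits that sentence, and SAP 5.7 does not list the omission as a change.

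**Step 4. Illustrative size.** Tabulated dengue status uses anti-NS1 IgG (positive at 9 ELISA units/mL or more, SAP 4.4.2.3), whereas the stop uses PRNT. Let q be the PRNT-negative share, a the anti-NS1-negative share among PRNT-negatives, and b the same share among PRNT-positives. All three are assumptions. With no other PPAS losses:

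- non-immune share, all subjects = q·a + (1 − q)·b
- non-immune share, PPAS without PRNT-negatives = b

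For q = 5%, a = 90%, b = 5%: 0.05 × 0.90 + 0.95 × 0.05 = 0.0925, or 9.3%, against 5.0%. About 150 × 0.05 = 7.5 subjects are dropped.

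| q | Dropped of 150 | All subjects, a = 90% | All subjects, a = 50% | PPAS (b = 5%) |
|---|---|---|---|---|
| 2% | 3 | 6.7% | 5.9% | 5.0% |
| 5% | 7.5 | 9.3% | 7.3% | 5.0% |
| 10% | 15 | 13.5% | 9.5% | 5.0% |
| 15% | 22.5 | 17.8% | 11.8% | 5.0% |

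The difference is q·(a − b). It is positive whenever PRNT-negative subjects are more often anti-NS1 negative than the rest, and zero if the two assays are unrelated.

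**Step 5. Other post-baseline losses.** These affect both sets and all three viruses. Suppose 90% of retained subjects are immune and a fraction l of the 150 is lost. The share among all 150 then lies between 0.9(1 − l) and 0.9(1 − l) + l: 81% to 91% for l = 10%, 72% to 92% for 20%, and 63% to 93% for 30%. These are worst-case limits and give no direction.

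**The case against.** Several counter-arguments have force.

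- **The FAS run shows these subjects.** This stands. The SAP requires that run, and the PRNT stop does not remove anyone from it. A reader might infer that both immunogenicity sets drop PRNT-negative subjects; the Visit 4 timing shows that only the PPAS can. The FAS still leaves out anyone without a valid post-injection result.
- **There may be more than one PPAS.** SAP 5.2.2 still speaks of a corresponding population, which suggests the per-vaccination sets were meant to survive. It also calls its list protocol deviations, and a stop required by the protocol may not be one. Both readings are possible and the text settles neither. Even a dose-1 set would drop a subject for a late Visit 4 sample.
- **Safety-set displays may exist.** Baseline characteristics are also shown on the safety set (SafAS), and SAP 5.1.4 plans safety tables by baseline status. It would therefore be too strong to say that the screening false positives are hidden. Neither section assigns the observational objective to the safety set, however.
- **The size cannot be known.** This stands. A reader might infer that the PPAS table would show 100% dengue-immune. That needs every retained PRNT-positive subject to be anti-NS1 positive, and the documents do not say so. If 7 of 142 retained subjects were anti-NS1 negative, the PPAS would show 135/142 = 95.1%.
- **YF and Zika.** Nothing in the documents links either status to completing the schedule, so no direction of bias can be claimed for them.

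**Conclusion.** The concern holds in a limited form. As written, the lead table for a description of the study population at baseline is on a set that requires irrelevant post-baseline data. On a literal reading of SAP 5.2.2, that set also excludes subjects because of their baseline PRNT result, so the table tends to understate the dengue non-immune share.

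The direction rests on one assumption: that PRNT-negative subjects are more often anti-NS1 negative than PRNT-positive subjects. The size is unknown. The 9.3% against 5.0% comparison is an illustration on assumed rates, not an estimate. The PRNT-stop mechanism concerns the PPAS only.

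Severity is minor. No hypothesis is tested, and no primary or secondary endpoint or sample-size figure changes.

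**What to change.** Two text changes to the SAP:

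1. In 5.2.5, state that baseline anti-NS1, YF and Zika results, and the derived dengue, YF, Zika and overall flavivirus statuses, are summarized primarily on all Randomized subjects with a valid Visit 1 sample, by group and overall. PPAS and FAS versions are supportive.
2. Reconcile 5.2.2 with Protocol 12.2.3: say whether a per-protocol set exists for each vaccination, and how subjects stopped for a negative baseline PRNT are classified in it. If the per-vaccination sets were dropped on purpose, list that in 5.7.

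The cost is a few sentences and one change of denominator. The Randomized set is already defined in SAP 5.2.4, and the Visit 1 sample is already planned for every subject. No new data are needed.

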5.3 Handling of Missing Data and Outliers

5.3.1 Safety

Generally, no replacement will be done for Safety Missing Data and Outliers.

5.3.1.1 Immediate

For unsolicited systemic AEs, a missing response to the “Immediate” field is assumed to have occurred after the 30-minute surveillance period and will not be imputed.

5.3.1.2 Causality

Missing causality (relationship) for unsolicited AEs and SAEs will be considered at the time of analysis as related to vaccination. The missing relationship to study procedures for SAEs will not be imputed.

5.3.1.3 Measurements

Missing measurement (for temperature or length) will not be replaced.

5.3.1.4 Intensity

For solicited reactions, missing intensities will be handled as described in [Section 4.4.1.1.1](#). For unsolicited AEs, missing intensities will remain missing and will not be imputed.

5.3.1.5 Start Date and Stop Date

Missing or partially missing start dates for unsolicited AEs will remain missing and not be imputed. If the start is missing or partially missing, the time of onset will be considered to be missing. Nevertheless, unsolicited AEs with missing time of onset will be included in analyses according to the visit number collected in “Appeared after visit” or similar field. If either the start date or end date is missing or partially missing, the duration will be considered missing.

Missing or partially missing stop dates for AEs (solicited reactions and unsolicited AEs) will remain missing and not be imputed.

5.3.1.6 Action Taken

Missing actions taken will remain missing and not be imputed.

5.3.2 Immunogenicity

No imputation of missing values and no search for outliers will be performed. LLOQ and ULOQ management will be performed as described in Section 4.4.2.1.

5.3.3 Efficacy

Not applicable.

5.4 Interim / Preliminary Analysis

No interim analysis will be performed as stated in section 5.7. A final analysis will be conducted once the 6-month safety data have been collected and the final database lock has occurred. No statistical adjustment is necessary because no hypotheses will be tested.

5.5 Determination of Sample Size and Power Calculation

The objective of the trial is to provide descriptive safety and immunogenicity results and therefore the sample size is arbitrarily set to 100 subjects for the CYD Dengue Vaccine Group and 50 subjects for the Placebo Group. There is a 95% probability of observing an event that has a true incidence rate of 3% for the CYD Dengue Vaccine Group.

5.6 Data Review for Statistical Purposes

A treatment blind review of the data has been anticipated through the data review process led by data management before database lock. This review of the data included a statistical review.

In the context of this study (ie, HIV-positive adults), a blinded early safety data review will be performed when the first 20 subjects have received the first injection and have provided safety data for Days 0-14 post-first injection on the following safety endpoints:

- Immediate (within 30 minutes) AEs
- Solicited injection site and systemic reactions
- Unsolicited AEs reported as related by the investigator within 14 days after the first injection
- SAEs and AESIs (including serious and non-serious AESIs)

5.7 Changes in the Conduct of the Trial or Planned Analyses

Subjects had other protocol violations that affected the subject's immune response (as determined by the clinical team before locking the database) has been added as one of the criteria for the PPAS definition in [Section 5.2.2](#) taking the study population being HIV-positive adults treated with ARTs into account.

The age computed automatically in the eCRF, and presented as an integer.

The Sponsor decided to add a second test, with a higher sensitivity, ie, an ELISA (Anti-Dengue IgG ELISA commercialized by Euroimmun) to screen potential study participants. Both tests are very specific. The two tests will be performed sequentially. RDT will be performed first, and IgG ELISA will only be performed on subjects who tested negative for RDT. These changes are presented in details in [Section 3](#).

Some endpoints derivation were updated in Section [4.4.1.2.2](#), [4.4.1.5.6](#) and [5.3.1.5](#) per latest Safety Task Force Guideline 8.0.

No interim analysis on data obtained up to Day 28 after the last injection of the last subject will be performed. The full trial results will be released in once in the final CSR.

6 References List

- 1 Gubler DJ. Dengue. In: Epidemiology of arthropod-borne viral disease. Monath TPM, editor, Boca Raton (FL): CRC Press, 1988:223-60
- 2 World Health Organization. Dengue and dengue haemorrhagic fever, Fact sheet N°117, Updated May 2015. [Accessed on 24 November 2015]. Available from URL: <http://www.who.int/mediacentre/factsheets/fs117/en/>
- 3 World Health Organization. Guidelines on the quality, safety and efficacy of dengue tetravalent vaccines (live, attenuated). WHO Expert Committee on Biological Standardization. WHO Technical Report Series No. 979, 2013. Annex 2
- 4 World Health Organization. Dengue: Guidelines for diagnosis, treatment, prevention and control. Geneva: WHO Press. 2009. WHO/HTM/NTD/DEN/2009.1
